2.3.2 Exclusion Criteria

Subjects will not be enrolled if any of the following criteria exist:

1. Hypersensitivity to pregabalin.
2. Current treatment with pregabalin.
3. CIPN that may be associated with previous treatment with a vinca alkaloid (e.g. vincristine, vinblastine), or current treatment with a vinca alkaloid.
4. History of diabetes mellitus or a neurological disorder with any previous signs of distal symmetric polyneuropathy.
5. Moderate to severe renal failure (Clcr < 30mL/min).

6. ALT (SGPT) or AST (SGOT) > 3 times the upper limit of normal.
7. Planned surgeries or radiation treatment within 10 weeks following study inclusion.
8. Inability to complete pain self-report.
9. Pregnancy or lactation
10. Patients with seizure disorders treated with anticonvulsants
11. Current participation in a trial with another investigational agent, unless co-enrollment is approved by the PIs of both studies.
12. Concomitant medication as follows:
 - Subjects treated with gabapentin or other anticonvulsant for neuropathic pain will be required to taper the medication and discontinue for at least 2 weeks prior to study initiation.
 - Patients on antidepressant treatment for pain or depression (TCAs, SSRI, SNRIs etc. will be allowed to continue their medications provided they have been on a stable dose for at least 4 weeks before study initiation. No dose regimen changes of antidepressants will be allowed during the study period.
 - Patients on around-the clock opioid treatment (including tramadol) will be allowed to continue their medication provided they have been on a stable dose for at least 4 weeks before study initiation. The maximum allowed dose of opioid will be equivalent to 60mg oral morphine sulphate. Patients with higher doses will be required to taper down their opioid dose to maximum 60mg oral morphine equivalent, and continue on stable dose for 4 weeks before enrollment in the study. PRN short-acting opioids for painful CIPN treatment will not be allowed. Patients receiving PRN short-acting opioids (with or without acetaminophen) for pain other than CIPN will be allowed up to 4 daily doses, with daily recording of analgesic consumption.
 - Treatment with NSAIDs will be discontinued at least 2 weeks before study initiation. However, low-dose aspirin (≤ 325 mg/day) will be allowed.

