1. SYNOPSIS

Study Title	Investigation of somatosensory predictors of response to pregabalin in painful chemotherapy-induced peripheral neuropathy (CIPN).
Objective	In a prospective, randomized, double-blind, cross-over study, to determine the correlation between mechanical pain threshold (MPT) at baseline and analgesic response to 4-week treatment with pregabalin vs. placebo in patients with painful CIPN.
Hypothesis	Increased mechanical hypersensitivity to pinprick (lower mechanical pain threshold (MPT)) corresponds to better analgesic response to pregabalin treatment in painful CIPN.
Study Period	Planned enrollment duration: Approximately 18 months Planned study duration: 10 weeks per subject; 4 weeks duration per arm, with 2 weeks washout between the two treatments.
Number of Patients	35 evaluable patients with painful CIPN
Study Treatment	Oral pregabalin (or matching placebo) administered BID and titrated to individual response in a dose up to 600mg/day. In subjects with CrCL of 30-60 mL/min, the dose will be limited to 300mg/day.
Study Design	Prospective, randomized, double-blind, placebo-controlled, cross-over study.
Inclusion and Exclusion Criteria	
Inclusion criteria:
 
 1. Age >18 2. Distal symmetric pain distribution (both feet, with or without pain in hands). 3. The pain appeared during or up to 12 weeks after treatment with oxaliplatin, paclitaxel, docetaxel or any combination of these. 4. Score of 4 or more on DN4 neuropathic pain questionnaire 5. Pain duration > 2 months. 6. Patient report of average daily pain intensity in the last week >3 on 0-10 Numerical Rating Scale (NRS). 7. Women of childbearing potential and men must agree to use adequate contraception (hormonal or barrier method of birth control, abstinence) prior to study entry and for the duration of study participation. 8. Able and willing to sign an IRB-approved written informed consent. 
Exclusion criteria:
 
 1. Hypersensitivity to pregabalin. 2. Current treatment with pregabalin. 3. Current treatment with a vinca alkaloid (e.g. vincristine, vinblastine), or CIPN that may be associated with previous treatment with a vinca alkaloid. 4. History of diabetes mellitus or a neurological disorder with any

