2.3.1 Inclusion Criteria

Inclusion criteria:

1. Age >18
2. Distal symmetric pain distribution (both feet, with or without pain in hands).
3. Pain appeared during or up to 12 weeks after treatment with oxaliplatin, paclitaxel, docetaxel or any combination of these.
4. Score of 4 or more on DN4 neuropathic pain questionnaire (Bouhassira, Attal et al. 2005).
5. Pain duration > 2 months.
6. Patient report of average daily pain intensity >3 on 0-10 Numerical Rating Scale (NRS) in the past week.
7. Women of childbearing potential and men must agree to use adequate contraception (hormonal or barrier method of birth control, abstinence) prior to study entry and for the duration of study participation. Should a woman become pregnant or suspect she is pregnant while participating in this study, she must inform her treating physician immediately.
8. Able and willing to sign an IRB-approved written informed consent.

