2.4.2 Pre-Study Period

At the screening visit, after obtaining signed informed consent, we will collect patient demographic data including details on cancer type and status, chemotherapy regimen(s) and cumulative doses, history of chronic pain, concomitant diseases and medication, and duration of painful CIPN. A blood sample for CMP will be obtained for determining serum creatinine concentration and liver transaminases (ALT and AST). If subject's lab tests results are available within the past 30 days, we will utilize these without the need of obtaining new renal and hepatic function tests. In addition, the patients will complete the following questionnaires: Brief Pain Inventory (BPI), Neuropathic Pain Symptom Inventory (NPSI), and Depression Anxiety and Positive Outlook Scale (DAPOS). Average and maximum daily pain intensity in the past week will be recorded as baseline pain intensity measure.

The subjects' extremities will be mapped for spontaneous pain, and response to the following sensory stimulation: cold (20°C Thermal Roller, Somedic), warm (40°C Thermal Roller, Somedic), pinprick (# 5.88 Semmes-Weinstein monofilament, 60mN target force, North Coast) and brush (SenseLab 0.5 brush, Somedic) (Finnerup, Sorensen et al. 2007). The probability of neuropathic pain will be graded as possible, probable, or definite according to Treede et al. criteria (Treede, Jensen et al. 2008). The results of sensory mapping will provide the information for the criterion on presence of any objectively tested positive or negative neurological signs in the painful territory. Photographs of the mapped extremities will be taken (in a way not to include any part of the subjects' face or other identifying information), for accurate reproduction of areas of sensory disturbance.

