3.2 Premature Discontinuation

If a subject chooses to discontinue treatment during the first treatment phase, he/she has the possibility either to withdraw from the study, or to continue the second phase of the study after a 2 week washout period.

Subjects will be withdrawn if they undergo a major surgery during the study period (any surgery that requires 2 or more days of hospitalization).

Subjects will be withdrawn from the study if during the study period they are placed on chemotherapy regimen that includes a taxane, a platinum compound or a vinca alkaloid.

Subjects will be withdrawn from the study if they require an increase in their other analgesic drugs, including chronic around-the-clock opioid dose; or need more than 4 PRN daily doses of a short-acting opioid.

Subjects will be withdrawn from the study in case of any of the following adverse events:

- Angioedema
- Hypersensitivity
- Suicidal behavior or ideation
- Peripheral edema in patients with New York Heart Association (NYHA) Class III or IV heart failure (in non-cardiac patients the peripheral edema due to pregabalin has not been associated with cardiovascular complications).

Subjects will be withdrawn if they experience any Grade 3 or higher adverse effect, if the investigator decides that discontinuation is in the best interest of the subject, or the subject requests withdrawal from the study.

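### Entry and withdrawal rules do not match for taxane and platinum chemotherapy, so the plan admits patients it must then withdraw and leaves those already on treatment unhandled

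*Combined protocol and SAP*

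**What the plan says.** **Entry.** Exclusion 3 in section 2.3.2 reads "CIPN that may be associated with previous treatment with a vinca alkaloid (e.g. vincristine, vinblastine), or current treatment with a vinca alkaloid". The synopsis has the same content in another order: "Current treatment with a vinca alkaloid (e.g. vincristine, vinblastine), or CIPN that may be associated with previous treatment with a vinca alkaloid". Neither names a taxane or a platinum compound. Inclusion 3 in section 2.3.1 is "Pain appeared during or up to 12 weeks after treatment with oxaliplatin, paclitaxel, docetaxel or any combination of these", and inclusion 5 is "Pain duration > 2 months". Neither asks that the causative drug has been stopped or sets a minimum time since the last dose.

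**Looking ahead.** Exclusion 7 is "Planned surgeries or radiation treatment within 10 weeks following study inclusion". Chemotherapy is not listed.

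**Screening data.** Section 2.4.2 collects "details on cancer type and status, chemotherapy regimen(s) and cumulative doses", but no eligibility criterion refers to planned or continuing taxane or platinum treatment.

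**Withdrawal.** Section 3.2 withdraws subjects "if during the study period they are placed on chemotherapy regimen that includes a taxane, a platinum compound or a vinca alkaloid".

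**Analysis.** Section 2.4.7 relates the percentage pain reduction in each treatment phase, taken from baseline pain, to baseline MPT and compares the two slopes. It specifies no period or sequence term. QST and pain are recorded again at Visit 3, before the second period (section 2.4.3 and Table 1), but section 2.4.7 gives those values no role in the primary analysis.

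**The concern.** The plan regards starting any of three drug classes during the study as incompatible with staying in it, yet at entry it screens for only one, and only as current treatment. The two classes left out include the drugs that define the study population, so the gap concerns the patients most likely to present.

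Two things are at stake. First, some patients can be randomised when it is already known at screening that they will have to leave, and each costs a pair in a small cross-over. Second, if patients still receiving a neurotoxic drug remain in, their neuropathy may change between the two periods. Section 2.1 itself says that severity depends on cumulative dose and length of therapy, and that early neuropathy can become chronic. Response in both periods is measured from one baseline, so a shift of that kind enters the outcome.

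**Working it through.** **Step 1. Entry rules set against the withdrawal rule**

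| Situation at screening | Entry criteria | Section 3.2 |
|---|---|---|
| Surgery planned within 10 weeks | Excluded (exclusion 7) | Withdrawn if major surgery takes place |
| Now on a vinca alkaloid | Excluded (exclusion 3) | Withdrawn if put on one during the study |
| Taxane or platinum course booked within 10 weeks | Not addressed, so eligible | Withdrawn once put on it |
| Now on a taxane or platinum drug | Not addressed, so eligible | Unclear |

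For surgery, both ends of the plan address the event. For taxanes and platinum compounds, only the withdrawal end does.

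The last row can be tested with a patient who has had 10 weeks of pain and is still receiving paclitaxel. Onset during treatment satisfies inclusion 3. Pain duration runs from onset, so inclusion 5 is met, and no exclusion on chemotherapy applies. Section 3.2 speaks of being placed on a regimen during the study, which most naturally means starting one. On that reading the patient stays, with exposure continuing. On a broader reading the patient is randomised and then withdrawn. The documents do not settle which.

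**Step 2. The plan's sample size**

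Inputs from section 2.4.8: difference 0.3, SD 0.5, alpha 0.05, power 85%, 27 required, 35 recruited, 20% dropout. Sidedness and test are not stated; I assume a two-sided paired t-test.

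- Standardised effect: 0.3 / 0.5 = 0.6.
- Power is the probability that a noncentral t variable, with n − 1 degrees of freedom and noncentrality 0.6 × √n, falls outside the two-sided 5% limits.
- At n = 27 the noncentrality is 0.6 × √27 = 3.12 and power is 85.1%. At n = 26 it is 83.6%. So 27 is the smallest n that reaches 85%, and the plan's figure reproduces.
- Dropout: 27 / 0.8 = 33.75, rounded up to 34; the plan recruits 35. Expected completers are 35 × 0.8 = 28, one more than needed.

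**Step 3. What lost pairs cost**

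| Complete pairs | Power |
|---|---|
| 28 | 86.4% |
| 27 | 85.1% |
| 26 | 83.6% |
| 24 | 80.4% |

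A loss of one to three pairs below 27 costs about 1.5 to 5 percentage points.

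**Step 4. What added noise could cost (illustration only)**

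The documents give no figure for change in the neuropathy under continuing exposure. Suppose it raised the SD of the within-patient difference, over the whole sample, by 10%, 20% or 30%. The standardised effect becomes 0.3/0.55 = 0.545, 0.3/0.60 = 0.50 or 0.3/0.65 = 0.46, and power with 27 pairs becomes 77.9%, 70.6% or 63.6%. These percentages are assumed. Inflation of that size across the whole sample would need more than slight change in one or two patients.

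**The case against.** The other side has several good points.

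- **Bias.** A reader might infer that disease progression would be mistaken for a drug effect. Sequence is randomised in blocks of 8 (section 2.4.1), so progression falls on pregabalin and placebo periods about equally. That holds even if progression is related to baseline MPT, since both slopes then shift alike in expectation. What remains is noise and chance imbalance in a small sample. This point stands.
- **A single baseline.** A reader might infer that MPT and pain are never checked again and that drift would go unseen. That is wrong: both are re-measured at Visit 3. What survives is narrower: the primary analysis as written uses only the baseline values.
- **An underpowered trial.** It is tempting to say that two such patients sink the sample size, because 0.8 × (35 − 2) = 26.4 is below 27. The documents do not support that. The count of two is assumed. It treats everyone already on treatment as withdrawn, which is the less natural reading of section 3.2. It stacks these losses on a 20% allowance that is not broken down by cause and may already include them. The synopsis and sections 2.3 and 2.4.1 also speak of 35 evaluable patients, whereas section 2.4.8 speaks of recruiting 35, so the base is uncertain. The cost in power is small in any case.
- **The vinca exclusion.** It might look like a stability rule that was not extended to the other drugs. Section 2.1 gives it a different rationale: animal data in which vincristine neuropathy did not respond to this drug class. The mismatch therefore lies between exclusions 3 and 7 on one side and section 3.2 on the other; it is not an omission within exclusion 3.

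None of this removes the gap for patients with a course already booked, or tells site staff what to do with a patient still on treatment.

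**Conclusion.** The concern holds as an inconsistency between entry and withdrawal rules, and that part rests on the text alone. A patient with a taxane or platinum course already scheduled within the 10 weeks is eligible, is randomised and must be withdrawn. A patient currently receiving such a drug is eligible, and the plan does not say whether they stay.

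The consequence is mainly lost pairs and extra within-patient variability. The documents do not support a claim of systematic bias between treatments, or of a trial that fails for want of power. The size cannot be derived, because the share of candidates on or scheduled for these drugs is not given. On the plan's inputs, read as a two-sided paired t-test, falling from 27 to 24 pairs takes power from 85.1% to 80.4%, and the dropout allowance may already absorb part of that. It is worth correcting because the loss is avoidable and cannot be repaired once patients are randomised.

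**What to change.** Before enrolment, reconcile the synopsis and sections 2.3.1, 2.3.2 and 3.2 on two matters.

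1. **Planned regimens.** Screen out at entry those patients whom the plan's own withdrawal rule would remove because of a regimen already planned for the study period. Exclusion 7 already supplies a 10-week horizon, and section 3.2 already supplies the list of drug classes.
2. **Patients already on treatment.** State, in the same terms at entry and at withdrawal, how a subject already receiving a taxane or platinum drug is handled. Which clinical rule applies to them is for the investigators to decide.

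The cost is a short eligibility amendment and slightly slower accrual. No new data collection should be needed beyond asking about planned treatment, since chemotherapy history is already taken at screening.

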2.4 Design and Procedures

2.4.1 Study Design

This is a prospective, randomized, double-blind, placebo-controlled, cross-over pilot study in 35 evaluable subjects with painful CIPN. If our hypothesis is confirmed, then patients with lower MPT at baseline will have larger analgesic effect with pregabalin than with placebo.

Registration, Randomization, and Blinding

Subjects that meet all criteria and wish to participate will be assigned study ID # and be randomized for the sequence of treatment for the study sessions. Patients may not start any protocol intervention until registration through the Siteman Cancer Center (SCC) is complete. The following steps will be taken before any study interventions occur: 1) confirmation of patient eligibility, 2) registration of patient in the SCC database, and 3) assignment of study ID #.

According to a computer-generated list of randomization numbers, the sequence of interventions will be determined: pregabalin and then matching placebo, or vice versa. Randomization will be performed by blocks of 8 subjects, without stratification. An unblinded

investigator will be assigned to match the study number with randomized treatment sequence, and this person will dispense the study medications. This investigator will not be involved at any stage at patient assessment, data collection or analysis. The participants and all other study personnel will be blinded to the treatment sequence allocation. At the end of the study, the subjects will be asked to complete a participant blinding questionnaire, to assess the risk of possible unmasking. As an additional approach to identify inadvertent failure in randomization or patient allocation, a single blood sample will be obtained at the last visit of each session, to determine the presence of pregabalin in plasma in patients allocated to pregabalin, and lack of drug in the placebo arm.

2.4.2 Pre-Study Period

At the screening visit, after obtaining signed informed consent, we will collect patient demographic data including details on cancer type and status, chemotherapy regimen(s) and cumulative doses, history of chronic pain, concomitant diseases and medication, and duration of painful CIPN. A blood sample for CMP will be obtained for determining serum creatinine concentration and liver transaminases (ALT and AST). If subject's lab tests results are available within the past 30 days, we will utilize these without the need of obtaining new renal and hepatic function tests. In addition, the patients will complete the following questionnaires: Brief Pain Inventory (BPI), Neuropathic Pain Symptom Inventory (NPSI), and Depression Anxiety and Positive Outlook Scale (DAPOS). Average and maximum daily pain intensity in the past week will be recorded as baseline pain intensity measure.

The subjects' extremities will be mapped for spontaneous pain, and response to the following sensory stimulation: cold (20°C Thermal Roller, Somedic), warm (40°C Thermal Roller, Somedic), pinprick (# 5.88 Semmes-Weinstein monofilament, 60mN target force, North Coast) and brush (SenseLab 0.5 brush, Somedic) (Finnerup, Sorensen et al. 2007). The probability of neuropathic pain will be graded as possible, probable, or definite according to Treede et al. criteria (Treede, Jensen et al. 2008). The results of sensory mapping will provide the information for the criterion on presence of any objectively tested positive or negative neurological signs in the painful territory. Photographs of the mapped extremities will be taken (in a way not to include any part of the subjects' face or other identifying information), for accurate reproduction of areas of sensory disturbance.

The subjects will undergo a quantitative sensory testing (QST) procedure to determine the MPT parameter (Maier, Baron et al. 2010). MPT will be measured using standardized weighted metal probes (Nervetest, MRC systems) using a modified method of levels (Haroutounian, Nikolajsen et al. 2014, Haroutounian, Nikolajsen et al. 2014). Several other QST measures will be obtained to better characterize the underlying nerve damage, and to provide additional factors to be incorporated in multiple regression analysis of predictors of response to pregabalin in CIPN. Namely, we will determine cold and warm detection thresholds (CDT and WDT), as well as cold and heat pain thresholds (CPT and HPT) with Thermal Sensory Analyzer (TSA-II, Medoc) using the method of limits. We will also assess the existence of paradoxical heat sensations (PHS) with TSA-II device, per standard protocol (Maier, Baron et al. 2010, Haroutounian, Nikolajsen et al. 2014) and will calculate the warm sensibility index (WSI) from the WDT and HPT values (Jensen, Bach et al. 1991). We will also test for temporal summation (TS) to mechanical stimulation (with 256mN pinprick probe), per standard protocol (Haroutounian, Nikolajsen et al. 2014) as a surrogate measure for central sensitization which has been implied to be important in determining effectiveness of Ca²⁺ channel $\alpha 2\delta$ subunit ligands.

In addition, we will apply conditioned pain modulation (CPM) protocol to assess the efficiency of individual descending noxious inhibitory pain controls, as this was previously suggested

to predict response to treatment in neuropathic pain (Yarnitsky, Granot et al. 2012). CPM protocol will test whether concomitant application (conditioning) of a mildly painful stimulus to an upper extremity (heat that elicits individually calibrated pain intensity of 30 on 0-100 NRS), reduces the painful experience from a painful (test) stimulus applied to the contralateral extremity (a thermal stimulus at temperature previously calibrated to elicit pain with intensity of 60 on 0-100 scale). Reduction of reported pain experience to test stimulus during conditioning is a surrogate measure of efficient descending pain modulation.

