The mechanisms of nerve injury in CIPN, and the transition from acute to chronic phase of neurotoxicity, are not fully understood. The patients present with peripheral nerve fiber degeneration and hyperexcitability, and one of the leading theories regarding the causation is related to the mitotoxic effects of chemotherapy on somatosensory afferent neurons. Despite differences in mechanisms of action, the different chemotherapy agents share some of the pathological findings in CIPN, e.g. common final pathway of axonal mitochondria damage. In addition, preclinical data suggest that CIPN caused by oxaliplatin and taxanes (paclitaxel and docetaxel) results in overexpression of $\alpha 2\delta$ subunits of voltage-gated Ca^{2+} channels in the dorsal root ganglion (DRG) and spinal cord dorsal horn in rats. This may imply that modulating neuronal Ca^{2+} channel function by $\alpha 2\delta$ ligands may be effective in treating CIPN caused by oxaliplatin and taxane compounds. Indeed, in preclinical studies administration of gabapentin (Lynch, Wade et al. 2004, Ling, Authier et al. 2007, Xiao, Boroujerdi et al. 2007) and pregabalin (Peng, Xi et al. 2012, Aoki, Kurauchi et al. 2014) has been demonstrated to successfully reduce mechanical and thermal hypersensitivity in rat models of CIPN induced by these compounds. Although CIPN induced by different drugs may result in a similar symptom pattern, the underlying mechanisms may vary. In mice, treatment with paclitaxel and oxaliplatin increases the DRG expression of $\alpha 2\delta$ mRNA, while treatment with vincristine does not result in similar changes. In addition, treatment with $\alpha 2\delta$ subunit ligand gabapentin was effective in mice with paclitaxel and oxaliplatin-induced mechanical allodynia, but not in vincristine-induced mechanical allodynia (Gauchan, Andoh et al. 2009). Thus, preclinical data suggests that $\alpha 2\delta$ subunit

of voltage-gated Ca^{2+} channels is a promising target for attenuating oxaliplatin- and taxane- induced CIPN.

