Patients will complete an electronic diary with daily report of their average and maximum daily pain intensity, recorded every evening before bedtime. The percentage of pain reduction for primary outcome will be assessed from the difference between baseline average pain intensity and the average pain intensity of last 5 days of treatment (day 24-28), on 0-10 NRS.

Secondary efficacy outcomes will include: 1) The difference between baseline maximum pain intensity and the maximum pain intensity of the last 5 days of treatment, on 0-10 NRS; 2) The proportion of patients achieving 50% or more pain relief with pregabalin vs. placebo treatment; 3) Difference in Pain Severity and Pain Interference scales of the BPI, assessed at baseline and day 28 of treatment. The daily use of rescue analgesia (oral acetaminophen) will also be recorded.

Table 1. Data assessment schedule

Required Assessments	Screening and Enrollment Baseline Visit	Week 1a	Week 2a	Week 3a	Week 4a	End of Treatment A (Day 28 +/- 2)	Wash-out	Study crossover visit	Week 1b	Week 2b	Week 3b	Week 4b	End of Study Visit (Day 30 +/- 3)
Study visits	Visit1 (a/b)*					Visit2		Visit3					Visit 4
Informed consent	✓												
Pregnancy (urine Hbhcg) test for women	✓												
Comprehensive Metabolic Panel (CMP) blood test**	✓					✓							✓
Inclusion/exclusion criteria	✓												
Randomization	✓												
Demographic data collection	✓												
Sensory Mapping	✓					✓		✓					✓
BPI questionnaire	✓				✓			✓				✓	
NPSI questionnaire	✓				✓			✓				✓	
DAPOS questionnaire	✓				✓			✓				✓	
SPI questionnaire	✓				✓			✓				✓	
QST	✓							✓					
CPM	✓							✓					
Dispense study drug	✓							✓					
Pain intensity 0-10 NRS	✓	daily	daily	daily	daily			✓	daily	daily	daily	daily	✓
Adverse Event assessment		daily	daily	daily	daily				daily	daily	daily	daily	✓
Telephone communication		weekly	weekly	weekly	weekly				weekly	weekly	weekly	weekly	
Blinding questionnaire***		✓											
Pill count								✓					✓
Blood sample (PK)						✓							✓
Skin biopsy (optional)													✓

*Visit 1 may be conducted over 2 visits to complete all assessments if required for subject tolerability or convenience

** A blood sample for CMP will not be obtained if recent (<30 days) results are available.

*** Blinding questionnaire to be administered via EMA device on Day 5 of study drug treatment

Subject Blinding Perception

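### Baseline pain is a single past-week recall while the outcome is a daily-diary mean, and nothing requires baseline pain or MPT to be measured after the medication washout

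*Combined protocol and SAP*

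**What the plan says.** **Baseline pain.** Section 2.4.2 opens "At the screening visit, after obtaining signed informed consent" and then states: "Average and maximum daily pain intensity in the past week will be recorded as baseline pain intensity measure". Inclusion criterion 6 uses the same quantity: patient-reported average daily pain over the past week must exceed 3.

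**Baseline MPT.** The same pre-study section states: "The subjects will undergo a quantitative sensory testing (QST) procedure to determine the MPT parameter".

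**Outcome.** Section 2.4.3 takes percentage reduction from baseline average pain and "the average pain intensity of last 5 days of treatment (day 24-28"). Section 2.4.7 takes the day 24-28 values from the patient diaries. Table 1 has one pain entry at Visit 1 and daily entries only in the treatment weeks.

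**Washout.** Under section 2.3.2, patients on gabapentin or another anticonvulsant for neuropathic pain "will be required to taper the medication and discontinue for at least 2 weeks prior to study initiation". NSAIDs have the same two-week condition. Section 2.4.10 repeats both. Study initiation is not defined.

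**Visit 1.** A footnote to Table 1 says: "Visit 1 may be conducted over 2 visits to complete all assessments if required for subject tolerability or convenience". It gives no window and does not allocate QST or the pain rating to 1a or 1b.

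**Visit 3.** Pain rating and QST are repeated before period 2. Their role as a baseline is not stated.

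**The concern.** There are two separate issues.

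1. **Instrument.** A one-off recall and a mean of daily entries can differ even in a patient whose pain has not changed. Any gap between them enters every percentage reduction and moves patients across the 50% threshold. Because the recalled value also decides entry, patients are selected on the number that later serves as their reference.

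2. **Timing.** MPT is the only predictor in the primary test. Section 2.1 reports that gabapentin and pregabalin "successfully reduce mechanical and thermal hypersensitivity in rat models of CIPN", and mechanical hypersensitivity is what MPT is meant to capture. A patient tested before gabapentin has been withdrawn could be misplaced on the predictor axis and could also have a lowered baseline pain score. The plan's wording does not exclude this.

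At stake are the power of the slope comparison and the meaning of the single-arm slopes, responder proportions and NNT.

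**Working it through.** **1. The plan's own sample size.** Section 2.4.8 gives a difference of 0.3, SD 0.5, 85% power, alpha 0.05 and 27 participants in a cross-over. A two-sided paired t-test (noncentral t, noncentrality 0.3/0.5 × √27) gives 85.1% power at n = 27, so the figure reproduces. Allowing for dropout, 27/0.80 = 33.75, or 34. The plan recruits 35, which leaves 35 × 0.80 = 28 completers.

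**2. Error in MPT.** The documents give neither the share of patients on these drugs nor the size of any drug effect. Assumptions: a fraction f of patients is tested on drug, which shifts MPT by one probe step, independently of true MPT. Probe forces double, so a step is one log2 unit. The SD of MPT is s steps.

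- Slope factor = s²/(s² + f(1−f)).
- Correlation factor = the square root of that. It is the relevant factor because section 2.4.8 sizes the trial on correlation coefficients.

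| s | f | Slope factor | Correlation factor | Power, n = 27 |
|---|---|---|---|---|
| 1.5 | 0.2 | 2.25/2.41 = 0.934 | 0.966 | 83% |
| 1.5 | 0.4 | 2.25/2.49 = 0.904 | 0.951 | 81% |
| 1.0 | 0.2 | 1/1.16 = 0.862 | 0.928 | 80% |
| 1.0 | 0.4 | 1/1.24 = 0.806 | 0.898 | 77% |
| 2.0 | 0.2 | 4/4.16 = 0.962 | 0.981 | 84% |
| 2.0 | 0.4 | 4/4.24 = 0.943 | 0.971 | 83% |

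Power is recomputed with 0.3 × correlation factor and SD 0.5. The central case is 81-83%, with a range of 77-84%.

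**3. MPT and baseline pain together.** Simulation of the paired slope difference: N = 27, 20,000 runs, one baseline shared by both periods. Assumed: baseline 6 (SD 1.3), residual SD 1.3, mean drug effect 1 point.

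- No true MPT-by-treatment effect, 30% of patients on drug at baseline (MPT up 1 SD, pain down 1 point): single-arm slopes are −2.4 (pregabalin) and −3.1 (placebo). Their difference is 0.6 and the rejection rate is 5.2%.
- True effect in the hypothesised direction: the slope difference shrinks from −18.4 to −15.5 and power falls from 78% to 62%. With half that shift (0.5 SD, 0.5 point), power is 73%.
- Recall error alone (SD 1 point): power falls from 78% to 75%.

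The simulation starts at 78%, not the planned 85%, so only the changes are informative.

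**4. Responder threshold.** Suppose the diary mean would have been 5.

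- Recall of 5.5: an unchanged patient shows 0.5/5.5 = 9% reduction. The 50% threshold is 2.75, only 45% below 5.
- Recall of 6: an unchanged patient shows 1/6 = 17%. The threshold is 3, only 40% below 5.
- On-drug baseline of 5 where the off-drug value is 6, end pain 3: (5−3)/5 = 40% instead of (6−3)/6 = 50%.

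Recall above the diary and an on-drug baseline push in opposite directions. The net effect cannot be derived from the documents.

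**The case against.** **The documents also support a complete washout at baseline.** Section 2.3.2 lists the washout among conditions for enrolment, and section 2.4.1 randomises only subjects who meet all criteria. Table 1 puts eligibility, QST, pain rating, randomisation and dispensing in one Visit 1 column. If these happen together, patients are already off those drugs. This stands: a reader might infer that patients will be tested on gabapentin, but the documents do not say so. The gap is the missing sentence that would rule it out. Figure 1, cited for the design and QST timing, could not be seen.

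**Support for a drug effect on MPT is thin.** It is rat data on gabapentin and pregabalin. Section 2.1 also reports that the only published randomised gabapentin trial in CIPN was negative, and nothing says NSAIDs alter MPT. This stands, and it is why the shift is an assumption.

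**MPT scale.** Section 2.4.6 specifies a mean MPT with no log transform, so the calculation in steps is not on the plan's stated scale. This stands too.

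**Section 2.4.7 could be read as taking both pain values from diaries.** It cannot work that way, because no diary precedes treatment.

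**A shared baseline largely looks after itself.** If one baseline serves both periods, its error cancels in the paired comparison of absolute reduction and mainly rescales the primary contrast. This stands for those analyses. It does not rescue single-arm slopes or threshold-based proportions.

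**This is a pilot, and a run-in diary is good practice rather than a requirement.** That is fair. But the phones are already planned, and noise in the predictor cannot be removed at analysis.

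**Conclusion.** The instrument mismatch is certain from the text: recalled baseline, diary outcome, no pre-treatment diary. The timing gap is an omission. On-drug measurement is permitted by the wording and is not stated.

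The consequence is a noisier predictor and denominator. Power for the slope difference falls from 85% to about 81-83% under the central assumptions (20-40% affected, one-step shift, SD 1.5 steps), and to 77-84% across SDs of 1.0-2.0. Larger losses need larger assumed shifts in both MPT and pain. Recall error alone costs about 3 points. Single-arm slopes, 50% responder rates and NNT are distorted by an amount and in a direction the documents cannot settle.

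Three stronger readings are not supported. The primary test is not made prone to false positives, since simulated type I error stays near 5%. Not every percentage reduction is shifted by incomplete washout, only those of patients who were taking the drugs. Nor is baseline necessarily fixed at screening: pain and QST are repeated at Visit 3, and which baseline serves period 2 is unspecified.

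The change should be made because it is cheap, not because the primary conclusion is in serious danger.

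**What to change.** 1. **Diary baseline.** In sections 2.4.2 and 2.4.7 and Table 1, issue the EMA phone at Visit 1. Define baseline average and maximum pain as the means of 5-7 daily diary entries before the first dose. Keep the recalled past-week value for eligibility only.
2. **Timing.** Define study initiation. State that the baseline diary days and the MPT/QST are taken after the required washout is complete and before the first dose, using Visit 1b where needed.
3. **Period 2.** State whether this baseline or the Visit 3 measurement serves period 2.

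**Cost.** The first dose comes about one week later for every patient, including those who need no washout, because Visit 1 currently also dispenses study drug. Patients who need washout have a second baseline visit. The phones and the 1a/1b split already exist. The required sample size of 27 is unchanged. No change to washout length or to any clinical rule is proposed.
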